APPENDIX 3. INSULIN TO CARBOHYDRATE RATIO

Insulin-to-Carb Ratio

This ratio tells you how many grams of carb are covered by one unit of bolus insulin.

Use your insulin-to-carb ratio every time you eat a meal. You may use it with snacks if advised by your provider.

The starting insulin to carb ratio is calculated by using the **450 Rule**. Here's how it works:

- Determine your total daily dose (TDD) of insulin.
 - This includes both your meal time and basal insulin used within a day.
 - $TDD = \underline{\hspace{2cm}}$
- Divide 450 by the TDD to get your ratio.
 - $Insulin\ Carbohydrate\ Ratio = 450/TDD = \underline{\hspace{2cm}}$
- To use the ratio, add up the grams of carb that you plan to eat at your meal, and divide this number by your ratio to obtain your regular insulin dose.

Example 1:

Someone's TDD = 45 units (e.g., the total amount of say Humalog and Lente insulins they used per day). 450 divided by 45 = 10. Therefore, 10 grams of carbohydrate are covered by each unit of regular insulin.

The insulin to carbohydrate has a ratio of 1:10, meaning that 1 unit of regular insulin "covers" 10 grams of carbohydrate.

If you will be eating 70 grams of carbohydrate, then divide 70 by 10, which equals 7. This means that you would take 7 units of insulin to cover the 70 grams of carb.

Example 2:

Someone's TDD = 50 units (e.g., the total amount of say Humalog and Lente insulins they used per day). 450 divided by 50 equals 9. Therefore, 9 grams of carbohydrate are covered by each unit of regular insulin.

The insulin to carbohydrate the starting insulin to carb ratio is 1:9, meaning that 1 unit of regular insulin "covers" 9 grams of carbohydrate.

If you will be eating 72 grams of carbohydrate, then divide 72 by 9, which equals 8. This means that you would take 8 units of insulin to cover the 72 grams of carb.

Based upon your ratio, the accompanying tables may be helpful to estimate the regular insulin mealtime dose:

Insulin to Carbohydrate Ratio: ½:10 ½ unit of insulin for every 10 grams of carbohydrate	
Grams of Carbohydrates	Units of Insulin
6-15	0.5
16-25	1
26-35	1.5
36-45	2
46-55	2.5
56-65	3
66-75	3.5
76-85	4
86-95	4.5
96-105	5
106-115	5.5

Insulin to Carbohydrate Ratio: ½:12 ½ unit of insulin for every 12 grams of carbohydrate	
Grams of Carbohydrates	Units of Insulin
10-18	0.5
19-31	1
32-42	1.5
43-56	2
57-68	2.5
69-81	3
82-93	3.5
94-106	4
107-118	4.5
119-130	5
131-148	5.5

Insulin to Carbohydrate Ratio: 1/2:15 1/2 unit of insulin for every 15 grams of carbohydrate	
Grams of Carbohydrates	Units of Insulin
7-22	0.5
23-37	1
38-52	1.5
53-67	2
68-82	2.5
83-97	3
98-112	3.5
113-127	4
128-142	4.5
143-157	5
158-172	5.5

Insulin to Carbohydrate Ratio: 1/2:20 1/2 unit of insulin for every 20 grams of carbohydrate	
Grams of Carbohydrates	Units of Insulin
11-30	0.5
31-50	1
51-70	1.5
71-90	2
91-110	2.5
111-130	3
131-150	3.5
151-170	4
171-190	4.5
191-210	5

Insulin to Carbohydrate Ratio: 1/2:25 1/2 unit of insulin for every 25 grams of carbohydrate	
Grams of Carbohydrates	Units of Insulin
12-38	0.5
39-63	1
64-88	1.5
89-113	2
114-138	2.5
139-163	3
164-188	3.5
189-213	4
214-238	4.5
239-263	5
264-288	5.5

Insulin to Carbohydrate Ratio: 1/2:30 1/2 unit of insulin for every 30 grams of carbohydrate	
Grams of Carbohydrates	Units of Insulin
15-45	0.5
46-75	1
76-105	1.5
106-135	2
136-165	2.5
166-195	3
196-225	3.5
226-255	4
256-285	4.5
286-315	5
316-345	5.5

Insulin to Carbohydrate Ratio: 1/2:35 1/2 unit of insulin for every 30 grams of carbohydrate	
Grams of Carbohydrates	Units of Insulin
18-52	0.5
53-87	1
88-122	1.5
123-157	2
158-192	2.5
193-227	3
228-262	3.5
263-297	4
298-332	4.5
333-367	5
368-402	5.5

Insulin to Carbohydrate Ratio: 1/2:40 1/2 unit of insulin for every 40 grams of carbohydrate	
Grams of Carbohydrates	Units of Insulin
21-60	0.5
61-100	1
101-140	1.5
141-180	2
181-220	2.5
221-260	3
261-300	3.5
301-340	4
341-380	4.5
381-420	5
421-460	5.5

Insulin to Carbohydrate Ratio: 1:5 1 unit of insulin for every 5 grams of carbohydrate	
Grams of Carbohydrates	Units of Insulin
3-7	1
8-12	2
13-17	3
18-22	4
23-27	5
28-32	6
33-37	7
38-42	8
43-47	9
48-52	10
53-57	11
58-62	12
63-67	13
68-72	14
73-77	15
78-82	16
83-87	17
88-92	18

Insulin to Carbohydrate Ratio: 1:6 1 unit of insulin for every 6 grams of carbohydrate	
Grams of Carbohydrates	Units of Insulin
3-9	1
10-15	2
16-21	3
22-27	4
28-33	5
34-39	6
40-45	7
46-51	8
52-57	9
58-63	10
64-69	11
70-75	12
76-81	13
82-87	14
88-93	15
94-99	16
100-105	17
106-111	18

Insulin to Carbohydrate Ratio: 1:7 1 unit of insulin for every 7 grams of carbohydrate	
Grams of Carbohydrates	Units of Insulin
4-10	1
11-17	2
18-24	3
25-31	4
32-38	5
39-45	6
46-52	7
53-59	8
60-66	9
67-73	10
74-80	11
81-87	12
88-95	13
96-102	14
103-109	15
110-116	16
117-124	17
125-132	18

Insulin to Carbohydrate Ratio: 1:8 or 2:15 1 unit of insulin for every 8 grams of carbohydrate, or 2 units of insulin for every 15 grams of carbohydrate	
Grams of Carbohydrates	Units of Insulin
5-11	1
12-19	2
20-27	3
28-35	4
36-43	5
44-51	6
52-59	7
60-67	8
68-74	9
75-83	10
84-89	11
90-99	12
100-104	13
105-115	14

Insulin to Carbohydrate Ratio: 1:10 1 unit of insulin for every 10 grams of carbohydrate	
Grams of Carbohydrates	Units of Insulin
6-15	1
16-25	2
26-35	3
36-45	4
46-55	5
56-65	6
66-75	7
76-85	8
86-95	9
96-105	10
106-115	11
116-125	12
126-135	13
136-145	14

Insulin to Carbohydrate Ratio: 1:12 1 unit of insulin for every 12 grams of carbohydrate	
Grams of Carbohydrates	Units of Insulin
10-18	1
19-30	2
31-42	3
43-54	4
55-66	5
67-78	6
79-90	7
91-102	8
103-114	9
115-126	10
127-138	11
139-150	12
156-162	13

Insulin to Carbohydrate Ratio: 1:15 1 unit of insulin for every 15 grams of carbohydrate	
Grams of Carbohydrates	Units of Insulin
7-22	1
23-37	2
38-52	3
53-67	4
68-82	5
83-97	6
98-112	7
113-127	8

Insulin to Carbohydrate Ratio: 1:18 1 unit of insulin for every 18 grams of carbohydrate	
Grams of Carbohydrates	Units of Insulin
9-27	1
28-45	2
46-63	3
64-81	4
82-99	5
100-117	6
118-135	7
136-153	8

Insulin to Carbohydrate Ratio: 1:20 1 unit of insulin for every 20 grams of carbohydrate	
Grams of Carbohydrates	Units of Insulin
11-30	1
31-50	2
51-70	3
71-90	4
91-110	5
111-130	6
131-150	7
151-170	8

Insulin to Carbohydrate Ratio: 1:25 1 unit of insulin for every 25 grams of carbohydrate	
Grams of Carbohydrates	Units of Insulin
10-35	1
36-60	2
61-85	3
86-110	4
111-159	5
160-185	6

Insulin to Carbohydrate Ratio: 1:30 1 unit of insulin for every 30 grams of carbohydrate	
Grams of Carbohydrates	Units of Insulin
15-45	1
46-75	2
76-105	3
106-135	4
136-165	5
166-195	6

Insulin to Carbohydrate Ratio: 1:35 1 unit of insulin for every 35 grams of carbohydrate	
Grams of Carbohydrates	Units of Insulin
17-52	1
53-87	2
88-122	3
123-157	4
158-192	5
192-227	6

Insulin to Carbohydrate Ratio: 1:40 1 unit of insulin for every 40 grams of carbohydrate	
Grams of Carbohydrates	Units of Insulin
21-60	1
61-100	2
101-140	3
141-180	4
181-220	5
221-260	6

Insulin to Carbohydrate Ratio: 1:45 1 unit of insulin for every 45 grams of carbohydrate	
Grams of Carbohydrates	Units of Insulin
22-68	1
69-113	2
114-158	3
159-204	4
205-249	5
250-294	6

Source:

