9.1.2. Regular Insulin: Humulin® R (U-100) (regular insulin human injection)

The dose of regular insulin is to be based upon the subject's historical mealtime insulin dose (based upon the subject's historical carbohydrate: insulin ratio). Insulin is to be administered SC (in the abdomen, peri-umbilicus).

Note: The calculated insulin dose should be rounded to the closest whole unit. For rounding, if the digit to the right of the decimal is ≤ 4 , round down (example 4.3 units = 4 units). If the digit to the right of the decimal is ≥ 5 , round up (example 4.5 units = 5 units).

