9.1.3. Regular Insulin Plus Pramlintide

Regular insulin plus pramlintide is to be co-administered as separate injections.

The new insulin dose is to be based upon the subject's historical mealtime insulin dose (based upon the subject's historical carbohydrate: insulin ratio). This historical dose will be reduced by 50% to be the new insulin dose. The associated pramlintide dose will be calculated from the new dosage of insulin (eg, 9 µg pramlintide per 1 U of insulin). The dosage of pramlintide will then be adjusted to the nearest increment on the Symlin® pen (eg, nearest 15 µg increment).

Regular insulin plus pramlintide is to be administered SC (in the abdomen, peri-umbilicus). The separate, co-administered regular insulin and pramlintide injections should be given to opposite sides of the abdomen (ie, left and right peri-umbilicus, opposite quadrants).

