9.1.4. Study Drug Doses

All subjects will get flexible doses of insulin, pramlintide, and PRAM9. The dose of regular insulin is calculated to correspond to a ratio of 9 µg of pramlintide for every 1 unit of insulin. Additionally, the dose of regular insulin is calculated from the subject's insulin-to-carbohydrate

(I:C) ratio to match a 75-gram carbohydrate challenge. Rule 450 will be used for carbohydrate counting and insulin dose calculation in this study (see [Appendix 3](#)). [Table 5](#) presents study drug doses for each study cohort.

Table 5: Study Drugs Dosing

Calculated Insulin Dose (U) ^a Based on Subject I:C Ratio	Pramlintide + Regular Insulin Co-Administration Arm (Two Separate Injections)			PRAM9 Co-Formulation Acm (Single Injection) ^c	
	Regular Insulin Arm	Insulin Dose (U)	Insulin Dose (U)	Pramlintide Dose (μg) Modified for Symlin® Pen ^b	Insulin/Pramlintide Dose (U)
2	2	1		15	1
4	4	2		15	2
6	6	3		30	3
8	8	4		30	4
10	10	5		45	5
12	12	6		60	6
14	14	7		60	7

a: The calculated insulin dose, if necessary, will be rounded to the closest whole unit (example 4.5 units = 5 units).

b: The dosage of pramlintide should be adjusted to the nearest increment on the Symlin® pen (eg, nearest 15-μg increment).

c: Each unit of PRAM9 contains 1 unit of insulin and 9 μg of pramlintide.

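### At the fixed 75 g load, 4 of the 22 Appendix 3 look-up tables give an insulin dose 1 U away from the protocol's division-and-rounding rule, and the halving of odd doses is not specified

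*Protocol*

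**What the plan says.** Section 9.1.4 ties the regular insulin dose to the subject's insulin-to-carbohydrate "ratio to match a 75-gram carbohydrate challenge", invokes Rule 450 and refers the reader to Appendix 3. Appendix 3 gives the calculation: the ratio is 450 divided by the total daily dose, and for the carbohydrate to be eaten the subject should "divide this number by your ratio to obtain your regular insulin dose". It then adds that "the accompanying tables may be helpful to estimate the regular insulin mealtime dose" and prints 22 of them, 8 in half-unit steps and 14 in whole units. One of these, headed "1 unit of insulin for every 10 grams of carbohydrate", assigns 7 U to the band from 66 to 75 g.

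The rounding rule is in Section 9.1.2, under regular insulin: "The calculated insulin dose should be rounded to the closest whole unit". An exact half goes up; the example there is 4.5 U becoming 5 U. Footnote a to Table 5 repeats it for the full calculated dose: "The calculated insulin dose, if necessary, will be rounded to the closest whole unit".

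For the co-administration arm, Section 9.1.3 says "This historical dose will be reduced by 50% to be the new insulin dose". Section 9.1.1 states the same 50% reduction for PRAM9. Table 5 shows the full and halved doses side by side for calculated doses of 2, 4, 6, 8, 10, 12 and 14 U.

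**The concern.** Because the load is always 75 g, only one row of each Appendix 3 table can bear on this trial. In several tables 75 g is the first or last value of a band, which is where a banded table and a rounding rule are most likely to part. The 1:10 ratio is also the one used in Appendix 3's own first worked example (total daily dose 45 U), so the case a site is most likely to look up first gives two doses at the study load.

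The second gap concerns the halved dose. The trial compares full-dose regular insulin with two arms at half the insulin dose, and the primary endpoint is glucose exposure above 180 mg/dL. If sites halve odd doses differently, the intended 2:1 insulin contrast varies between subjects in a way the protocol would not flag as a deviation. With 18 subjects at up to 4 sites, that variation would be hard to see or adjust for. Hypoglycemia is an adverse event of special interest, so consistency of the insulin dose also matters for safety.

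**Working it through.** **Inputs.** Load 75 g (Section 9.1.4). Dose = grams / ratio (Appendix 3). Round to the closest whole unit, with .5 going up (Section 9.1.2; Table 5 footnote a). Reduction of 50% (Sections 9.1.1 and 9.1.3). Pramlintide 9 µg per unit of insulin, adjusted to the nearest 15 µg (Section 9.1.3).

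**Reproducing the plan's own figures.** The Appendix 3 examples check: 70/10 = 7 and 72/9 = 8. Table 5 checks in all 7 rows: halved doses 1 to 7 U give 9, 18, 27, 36, 45, 54 and 63 µg, which go to 15, 15, 30, 30, 45, 60 and 60 µg as printed.

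**Tables against the rule at 75 g.** Fifteen of the 22 tables show the rule's dose directly. The other seven are:

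| Ratio | Exact (75/ratio) | Rule | Table | Table entry after the same rounding |
|---|---|---|---|---|
| 1:6 | 12.5 | 13 | 12 | 12, differs |
| 1:8 | 9.375 | 9 | 10 | 10, differs |
| 1:10 | 7.5 | 8 | 7 | 7, differs |
| 1:30 | 2.5 | 3 | 2 | 2, differs |
| 1/2:10 | 3.75 | 4 | 3.5 | 4, agrees |
| 1/2:15 | 2.5 | 3 | 2.5 | 3, agrees |
| 1/2:25 | 1.5 | 2 | 1.5 | 2, agrees |

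Four tables therefore give a different whole-unit dose. Three of them (1:6, 1:10, 1:30) take an exact half down where Section 9.1.2 takes it up. The fourth is headed for both 1:8 and 2:15. At 2:15 the dose is 75 × 2/15 = 10 U, which matches the table, so the conflict exists only at 1:8. Each difference is 1 U; relative to the rule's dose that is 1/13 = 7.7%, 1/9 = 11.1%, 1/8 = 12.5% and 1/3 = 33.3% for 1:6, 1:8, 1:10 and 1:30.

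**Tables against each other.** 1/2:15 and 1:30 are the same ratio, but at 75 g they give 2.5 U and 2 U. 1/2:10 and 1:20 are the same ratio and give 3.5 U and 4 U. After rounding to whole units the second pair agrees (4 and 4); the first still does not (3 and 2).

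**Odd doses.** No row of Table 5 has an odd calculated dose. If, as an assumption, the halved dose D/2 were also rounded half-up, the reduction would be 1 − round(D/2)/D:

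- D = 3: 1 − 2/3 = 33.3%
- D = 5: 1 − 3/5 = 40.0%
- D = 7: 1 − 4/7 = 42.9%
- D = 9: 1 − 5/9 = 44.4%
- D = 11: 1 − 6/11 = 45.5%
- D = 13: 1 − 7/13 = 46.2%

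Even doses give exactly 50%. Under the same assumption the order of steps can matter. A calculated 4.5 U becomes 5, then 2.5, then 3 U if rounded first, but 2.25, then 2 U if halved first. A calculated 12.5 U becomes 7 U or 6 U in the same way.

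**How the two gaps meet.** In each of the four conflicts one candidate dose is even and the other odd (12 or 13, 10 or 9, 8 or 7, 2 or 3). The choice of source therefore decides whether Table 5 supplies a halved dose at all.

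**The case against.** The strongest reply is that the tables are not the dosing method. The protocol prescribes Rule 450, Appendix 3 carries it out by division (at 75 g this is simply total daily dose / 6), and the tables are offered only as an aid to estimation, in wording meant for patients. A real subject's ratio need not be one of those tabulated. This softens the conflict but does not remove it: Appendix 3 is the cited dosing source, and nothing says that the division prevails over the tables printed beneath it.

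Four stronger readings are tempting, and the document supports none of them.

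- A reader might count 7 conflicting tables. Three of those are half-unit entries that the Section 9.1.2 rule itself turns into the same whole-unit dose.
- A reader might infer that the 50% reduction fails for every odd dose. No passage says the halved dose is rounded: the rounding note is in the regular insulin section, and footnote a attaches to the full dose before halving. The reductions below 50% are conditional on that reading.
- A reader might infer that one arm is dosed from the tables and another from the formula. Table 5 derives all three arms from one calculated dose, so a look-up difference would carry through all arms of a subject's crossover and disturb the 2:1 ratio only through the handling of odd doses. PRAM9 and co-administration share the same halving instruction, so no insulin difference between those two arms is shown.
- A reader might infer that about half of subjects are affected. That needs an assumed odd/even split, for which the protocol gives no basis.

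**Conclusion.** The point holds as an internal contradiction plus an unfixed step. At the only carbohydrate load the trial uses, 4 of 22 Appendix 3 tables (3 if the dual-headed table is read at 2:15) are 1 U away from the division-and-rounding result, and two pairs of equal-ratio tables disagree as printed. These comparisons rest only on printed figures and the stated rule. The handling of odd doses under the 50% reduction, and the order of rounding and halving, are not stated. The shortfall from 50% depends on the assumption that halved doses are rounded half-up to whole units. How many subjects would be affected cannot be derived from the protocol. The sponsor should resolve this, because it bears on dose consistency across sites and on hypoglycemia risk.

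**What to change.** Reconcile Sections 9.1.1 to 9.1.4, Table 5 and Appendix 3 so that:

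- each ratio yields one dose at 75 g, from one source that the protocol names as governing;
- the handling of odd calculated doses under the 50% reduction, including the order of rounding and halving, is stated, is consistent with Table 5, and is the same for PRAM9 and co-administration.

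Which dose or rounding rule should prevail is for the sponsor and its clinical advisers. The cost is protocol and appendix wording only; no design element, assessment or sample size changes.
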